7.3 Exploratory outcomes

For the exploratory outcome analyses, results for the following outcomes will be used from both eyes to investigate if atropine has an effect on the outcomes. At baseline, the exploratory outcomes will only be presented as mean (SD) by treatment arm. For the following endpoints, the results will be compared between the atropine and placebo groups at all available timepoints using GEE (repeated measures model) and 95% CIs and will be adjusted for the corresponding baseline exploratory outcomes (if available). This includes; anterior chamber depth, accommodative lag at 33, 25 and 20cm and chorioretinal thickness. This also includes nasal and temporal results which will be looked at separately for each of the following outcomes; peripheral axial length (20°), ciliary body biometry, peripheral retinal defocus (20°) and peripheral retinal defocus (30°).

Descriptive statistics for height and weight will be presented by treatment arm at all available time points. Total hours of outdoor activity and binocular amplitude of accommodation will be compared between the atropine and placebo groups at all available time points using repeated measures

Doc No: ST06-RD01 Page **14** of **47**

ANCOVA and 95% CI and will be adjusted for the corresponding baseline exploratory outcome (if available). For hours of outdoor activity, this will firstly be summed together based on the outdoor activity totals for each of the weeks across the study, to give the total hours of outdoor activity at each of the available time points.

7.4 Subgroup analyses

Exploratory subgroup analyses will be performed on the primary outcome using 99% CIs and interaction terms (treatment group by subgroup) for the following subgroups: age (6-9 and 10-12 years at start of trial), ethnic background (white versus non-white), severity of myopia (less than -3D in either eye versus -3D or greater myopia), iris colour (Dark brown and Other including; light brown, green, blue and grey) and gender (male/female). The subgroup analyses will be performed using GEE and adjusted for baseline SER. The global test for interaction will be used for the interaction term.

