1.4 Inclusion and Exclusion Criteria

Patients will be eligible to participate in the study if they fulfil the following criteria below. Eligibility will be confirmed by a medically qualified doctor and documented on the eligibility checklist form.

Inclusion Criteria

- 1. Age 6-12 years (at the time of consenting)
- 2. Myopia of -0.5D or greater (spherical equivalent refractive error) in both eyes
- 3. Best-corrected distance visual acuity (BCDVA) 0.20 logMAR or better in both eyes

Exclusion Criteria

- 1. Children with other ocular morbidities
- 2. Myopia of -10D or greater in either eye
- 3. Astigmatism of 2D or higher in either eye
- 4. Amblyopia
- Significant health problems that can compromise the ability to attend research visits or complete the trial
- 6. Other factors that may compromise the ability to attend the research appointments
- 7. Parents or children with poor understanding of the English language
- 8. Children enrolled in other interventional trials*
- 9. Allergy or hypersensitivity to atropine or excipients
- 10. Previous use of atropine eye-drops, prior or current use of Ortho-K contact lenses or contact lenses with dual focus, multifocal or extended depth of focus lens design
- 11. Children or Parents / Guardians with latex allergy as the dropper used to administer the eye-drop contains latex

*Children enrolled in observational studies are potential candidates for CHAMP UK. Whether or not children enrolled in CHAMP UK are also involved in other observational studies is at the discretion of the CHAMP UK local Principal Investigator (PI) and should be considered when the burden on participants is not expected to be onerous. Coenrolment with other studies should be documented in the Case Report Form (CRF).

Full details of the background to the trial and its design are presented in the protocol.

Doc No: ST06-RD01 Page **6** of **47**

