8.3 Baseline Characteristics

- Minimisation factors, n (%) by treatment arm and total
- Gender, n (%) by treatment arm and total
- Age (years), mean (SD) by treatment arm and total
- Weight (kg), mean (SD) by treatment arm and total
- Height (cm), mean (SD) by treatment arm and total
- Ethnicity, no. (%) by treatment arm and total
- Parental myopia, no. (%) by treatment arm and total
- SER in both eyes, mean (SD) by treatment arm and total
- SER in left eye, mean (SD) by treatment arm and total
- SER in right eye, mean (SD) by treatment arm and total
- Central axial length in both eyes, mean (SD) by treatment arm and total
- Central axial length in left eye, mean (SD) by treatment arm and total
- Central axial length in right eye, mean (SD) by treatment arm and total
- EQ5D-Y- Visual Analogue Scale, mean (SD) by treatment arm and total
- EQ5D-Y- index score, mean (SD) by treatment arm and total
- Uniocular BCdVA in both eyes, mean (SD) by treatment arm and total
- Uniocular BCdVA in left eye, mean (SD) by treatment arm and total
- Uniocular BCdVA in right eye, mean (SD) by treatment arm and total
- Binocular BCdVA, mean (SD) by treatment arm and total
- Uniocular near VA in both eyes, mean (SD) by treatment arm and total
- Uniocular near VA in left eye, mean (SD) by treatment arm and total
- Uniocular near VA in right eye, mean (SD) by treatment arm and total
- Binocular near VA, mean (SD) by treatment arm and total
- · Reading speed, mean (SD) by treatment arm and total
- Pupil diameter in both eyes, mean (SD) by treatment arm and total
- Pupil diameter in left eve. mean (SD) by treatment arm and total
- Pupil diameter in right eye, mean (SD) by treatment arm and total
- Spectacle correction, no. (%) by treatment arm and total
- Frequency of spectacle correction; all day and sometimes, no. (%) by treatment arm and total
- Contact lens use, no. (%) by treatment arm and total
- Frequency of contact lens use; all day and sometimes, no. (%) by treatment arm and total

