8.7 Subgroup analyses

- SER at month 24 according to age group (6-9 and 10-12): mean (SD) by treatment arm, difference in means with 95% CI, p-value from GEE model, adjusted for baseline SER in ITT and PP analysis.
- SER at month 24 according to ethnicity group (white and non-white): mean (SD) by treatment arm, difference in means with 95% CI, p-value from GEE model, adjusted for baseline SER in ITT and PP analysis.

- SER at month 24 according to severity of myopia (less than -3D and -3D or greater): mean (SD) by treatment arm, difference in means with 95% CI, p-value from GEE model, adjusted for baseline SER in ITT and PP analysis.
- SER at month 24 according to iris colour (Dark brown and Other including; light brown, green, blue and grey): mean (SD) by treatment arm, difference in means with 95% CI, p-value from GEE model, adjusted for baseline SER in ITT and PP analysis.
- SER at month 24 according to gender (male/female): mean (SD) by treatment arm, difference in means with 95% CI, p-value from GEE model, adjusted for baseline SER in ITT and PP analysis.

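### Age and myopia severity are tested as effect modifiers only after each is cut in two; if modification is roughly linear, the cuts discard about 25-40% of the interaction information

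*Supplement*

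**What the plan says.** SAP section 7.4 sets the framework: "Exploratory subgroup analyses will be performed on the primary outcome using 99% CIs and interaction terms (treatment group by subgroup"). The subgroups it lists are "age (6-9 and 10-12 years at start of trial), ethnic background (white versus non-white), severity of myopia", iris colour and gender, with the severity split given as "severity of myopia (less than -3D in either eye versus -3D or greater myopia"). On the model it says: "The subgroup analyses will be performed using GEE and adjusted for baseline SER". Section 8.7 repeats the two-level groups, for example "SER at month 24 according to age group (6-9 and 10-12): mean (SD) by treatment arm", and so does the subgroup table in Appendix 1, which has one interaction p-value per subgroup factor.

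Both measures exist on a continuous scale. Section 8.3 summarises "Age (years), mean (SD) by treatment arm and total", and baseline SER is already a covariate in the subgroup GEE. Eligibility in section 1.4 is wide: "Age 6-12 years (at the time of consenting") and "Myopia of -0.5D or greater (spherical equivalent refractive error) in both eyes", with -10D or greater in either eye excluded. Section 6.1 uses the -3D split, but no age split, as a minimisation factor.

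**The concern.** A test on a two-level version of a continuous modifier treats a child of 6 like one of 9, and a child at -3D like one at -9D. If the treatment effect changes gradually with age or severity, the within-band part of that change is ignored and the test loses power. Interaction tests already have little power in a trial sized for its main effect. The risk is a non-significant interaction being read as evidence of a uniform effect when the collected data could have given a sharper answer.

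**Working it through.** **Inputs from SAP section 5.** SD 0.7 D, between-eye correlation 0.9, variance inflation factor 1.9, main effect 0.32 D, dropout 15%, 10% Chinese, 289 children at 2:1 (193 and 96). Section 7 gives p < 0.05, taken here as two-sided.

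**Reproducing the plan's figure.** Eyes per arm at 1:1: 2 x (1.960 + 1.282)^2 x 0.49 / 0.1024 = 100.6, so 101; x 1.9 / 2 = 96 children (the plan has 97, which 102 eyes would give). At 2:1: 76 + 152 = 228 eyes; x 1.9 / 2 = 216.6 children; / (1 - 0.15 - 0.10) = 288.8, so 289. The inputs are therefore understood as the plan uses them. The SAP states no interaction size and no interaction power.

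**Precision of the interaction.** SD of a child's two-eye mean = 0.7 x sqrt(1.9 / 2) = 0.682 D. Children analysed = 289 x 0.85 = 246. The SE of the interaction slope, per SD of the modifier, is 0.682 / sqrt(246 x 0.668 x 0.332) = 0.0924 D.

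**Information kept by a cut.** For a linear modifier this is the squared correlation between the measure and its two-group version. The SAP gives no distribution for age or SER, so the shapes below are assumptions.

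- Age uniform from 6 to just under 13, cut at 10: 3 x (4/7) x (3/7) = 0.735, a loss of 27% (25% if age is recorded in whole years).
- Age skewed to older children (triangular, 6 to 13, mode 11): 0.69 kept, a loss of 31%.
- Age truncated normal: a loss of about 33-34% for the two shapes nearest the middle of the range, up to 41% for others tried (mean 9-10, SD 1.5-1.9).
- Baseline SER truncated normal (mean -2.5 to -3.5 D, SD 1.5 to 2 D): 0.67 to 0.60 kept, a loss of 33-40%. Skewed shapes that were also tried lose 32-47%.

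**Power.** With z = slope x SD(modifier) / 0.0924, continuous power is about Phi(z - 1.96) and cut-scale power about Phi(z x sqrt(share kept) - 1.96). For uniform age, SD = 7 / sqrt(12) = 2.02 years, so the SE is 0.0924 / 2.02 = 0.0457 D per year. The bands' mean ages are 8 and 11.5, so the gap in treatment effect between bands is 3.5 x slope. For SER, the SD after truncation is 1.28 D (mean -2.5, SD 1.5) or 1.75 D (mean -3.5, SD 2), and the band means differ by 2.12 D or 2.82 D.

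| Modifier | Slope | Gap between bands (D) | Continuous | Cut | Loss (points) |
|---|---|---|---|---|---|
| Age, uniform | 0.05 D/year | 0.175 | 19.4% | 15.5% | 3.9 |
| Age, uniform | 0.08 D/year | 0.28 | 41.7% | 32.3% | 9.4 |
| Age, uniform | 0.10 D/year | 0.35 | 59.0% | 46.6% | 12.4 |
| Age, uniform | 0.12 D/year | 0.42 | 74.7% | 61.4% | 13.3 |
| SER, mean -2.5, SD 1.5 | 0.05 D per D | 0.11 | 10.6% | 8.7% | 1.9 |
| SER, mean -3.5, SD 2 | 0.05 D per D | 0.14 | 15.7% | 11.3% | 4.4 |
| SER, mean -2.5, SD 1.5 | 0.12 D per D | 0.25 | 38% | 27% | 11 |
| SER, mean -3.5, SD 2 | 0.12 D per D | 0.34 | 62% | 42% | 20 |

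At a gap of exactly 0.32 D, power falls from 52% to 40% for a uniform measure and from 58% to 41% for a normal one cut at its median. A simulation of 4000 trials at 0.10 D per year with uniform age gave 59% against 43%, slightly worse for the cut than the approximation.

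**The opposite case.** If the truth is a 0.32 D step exactly at the cut, the cut-scale test has 41% power and the continuous test about 32%.

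**The case against.** Five points on the other side carry weight.

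- The losses are conditional. A reader might infer that the cuts cost 10 to 15 points of power outright. The SAP does not support that, because it gives no age or SER distribution and no interaction size. A slope of 0.10 D per year makes the gap between bands (0.35 D) larger than the whole assumed main effect. With weaker modification the loss is only a few points.
- A reader might take the -3D cut as arbitrary. It is not: it is a minimisation factor, and analysing it on the scale used at randomisation is a recognised choice. That supports keeping and showing the groups, but it does not require the only test to be on that scale.
- The SAP refers to the protocol for full design details, and the protocol is not among the documents shown. The absence of a stated reason for the cut points is therefore not held against the plan.
- The analyses are labelled exploratory and use 99% CIs in section 7.4. Even on the continuous scale, power is only about 50-60% for a gap as large as the main effect, so a null interaction would be inconclusive either way.
- A linear term is itself an assumption, and it does worse than the cut if the true change is a step.

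The core remains: no continuous interaction is planned, the data for it are already collected, and under gradual modification the cut-scale test is the weaker one.

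**Conclusion.** The point holds as a conditional, low-severity improvement. Assuming a roughly linear modifier and the distributions above, the cuts discard about 25-40% of the interaction information: about 27-33% for age and 33-40% for severity, with some other shapes tried reaching 41% and 47%. This costs about 10-20 points of power when modification is about as large as the assumed 0.32 D effect, about 2-5 points when it is weak, and nothing if the effect changes in a step at the cut. The direction does not depend on the significance level: at 1%, the case of 0.10 D per year with uniform age gives about 35% against 24%. The documents do not support reading this as a threat to the primary analysis, or as showing that the planned subgroup tests are invalid.

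**What to change.** In sections 7.4 and 8.7, add two terms as the interaction tests for these modifiers: treatment by continuous baseline age, with age as a main effect, and treatment by continuous baseline SER. State which SER enters the interaction, for example the child's two-eye mean or the more myopic eye, because the severity group is defined per child while the GEE uses both eyes. Keep the 6-9 / 10-12 and -3D groups to display arm means and differences in the Appendix 1 table, and report their cut-scale interaction p-values alongside as a check on linearity. The cost is a sentence or two in each section, two model terms and two further exploratory p-values, plus the linearity assumption. No new data are needed.

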7.5 Additional analyses

Additional analyses will be performed on the primary and secondary outcomes to investigate any differences between atropine and placebo groups at all other available time points not previously analysed (i.e. 6, 12 and 18 months). The primary and secondary outcomes at baseline will only be presented by treatment arm in the PP analysis in this additional analyses, as the ITT baseline results are presented in the baseline characteristics table.

For the primary outcome SER, results will be used from both eyes and will be compared using GEE (repeated measures model) and 95% CIs and will be adjusted for baseline SER. Secondary analysis of the primary outcome will be adjusted for baseline SER and minimisation variables (i.e. site and ethnicity), baseline age and history of parental myopia (at least one parent).

For the secondary outcome analyses, results will be used from both eyes to investigate if atropine has an effect on the following endpoints; central axial length, pupil diameter, uniocular BCdVA and uniocular near VA. These endpoints will be compared between the two groups using GEE (repeated measures model) and 95% CIs and will be adjusted for the corresponding baseline secondary outcomes (if available). For the following endpoints; binocular BCdVA, binocular near VA, reading speed and quality of life (i.e. EQ-5D-Y VAS and Index) comparisons between the two groups will be performed using repeated measures ANCOVA and 95% CIs and will be adjusted for the corresponding baseline secondary outcome (if available).

Tolerability will be compared between the atropine and placebo groups using repeated measures ANOVA and 95% CI. Spectacle correction will be compared between the atropine and placebo groups using repeated measures generalised linear model. N(%) of spectacle correction (all day and sometimes) will also be presented by treatment arm.

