7.1 Primary outcome

The principal analysis will be based on complete case data without imputation for those who dropped out of the study before the end of the 24 months. The primary outcome (SER at month 24) results from both eyes will be used and adjusted for baseline SER. The atropine and control groups will be compared using generalised estimating equations (GEE) and 95% confidence intervals (CIs), to allow for the correlation between eyes within a participant. Secondary analysis of the primary outcome will be adjusted for baseline SER, minimisation variables (i.e. site and ethnicity), baseline age and history of parental myopia (at least one parent).

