7.6 Missing data

Sensitivity analyses will be undertaken to assess the impact of missing data for the primary outcome, by imputing extreme values of change within treatment arm (i.e. smallest and largest change from the previous time point to 24 months). Results between the atropine and placebo groups will be compared using GEE and 95% CIs and will be adjusted for baseline SER and also adjusted for baseline SER, minimisation variables (i.e site and ethnicity), baseline age and history of parental myopia (at least one parent). If the baseline primary outcome is missing, spectacle refraction based on the current prescription at baseline will be used in the sensitivity analysis.

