^a Adjusted for baseline SER. ^b Adjusted for baseline SER, minimisation variables (i.e. site and ethnicity), age and history of parental myopia (at least one parent). ^c Mean(SD) was calculated with data from both eyes. Mean difference estimate and p value from GEE. ^d Mean difference estimate and p value from ANCOVA. ^e Frequency (%) presented for categorical variables and risk difference and p value from the chi-square test (or fishers exact test if applicable). ^f Mean(SD) and p value from independent samples t-test, no adjustment as tolerability not measured at baseline.

Table XXX: Safety Outcomes by treatment group

	ı	Number of Events	S	Number of Patients						
	Total N=	Atropine sulfate N=	Placebo N=	Total N=	Atropine sulfate N=	Placebo N=	Risk Ratio (95% CI)	p-value		
Adverse Events	n (%)	n (%)	n (%)	n (%)	n (%)	n (%)	xx.x (x.x to x.x)	X.XX		
Adverse Reactions	n (%)	n (%)	n (%)	n (%)	n (%)	n (%)	xx.x (x.x to x.x)	X.XX		
Unexpected Adverse Reactions	n (%)	n (%)	n (%)	n (%)	n (%)	n (%)	xx.x (x.x to x.x)	x.xx		
Serious Adverse Events	n (%)	n (%)	n (%)	n (%)	n (%)	n (%)	xx.x (x.x to x.x)	x.xx		
Serious Adverse Reactions	n (%)	n (%)	n (%)	n (%)	n (%)	n (%)	xx.x (x.x to x.x)	x.xx		
Suspected Unexpected Serious Adverse Reactions	n (%)	n (%)	n (%)	n (%)	n (%)	n (%)	xx.x (x.x to x.x)	x.xx		
Fatal Serious Adverse Events	n (%)	n (%)	n (%)	n (%)	n (%)	n (%)	xx.x (x.x to x.x)	x.xx		

Table XXX: Safety outcomes by system organ class and treatment group

		Nu	ımber of Eve	nts	Number of Patients				
		Total	Atropine sulfate	Placebo	Total N=	Atropine sulfate N=	Placebo N=	RR (95%CI)	p-value
	Blood and lymphatic system disorders	n (%)	n (%)	n (%)	n (%)	n (%)	n (%)	xx.x (x.x to x.x)	x.xx
	Cardiac disorders	n (%)	n (%)	n (%)	n (%)	n (%)	n (%)	xx.x (x.x to x.x)	X.XX
	Gastrointestinal disorders	n (%)	n (%)	n (%)	n (%)	n (%)	n (%)	xx.x (x.x to x.x)	x.xx
AEs	Hepatobiliary disorders	n (%)	n (%)	n (%)	n (%)	n (%)	n (%)	xx.x (x.x to x.x)	x.xx
	Respiratory, thoracic and mediastinal disorders	n (%)	n (%)	n (%)	n (%)	n (%)	n (%)	xx.x (x.x to x.x)	x.xx
		n (%)	n (%)	n (%)	n (%)	n (%)	n (%)	xx.x (x.x to x.x)	X.XX
	Blood and lymphatic system disorders	n (%)	n (%)	n (%)	n (%)	n (%)	n (%)	xx.x (x.x to x.x)	x.xx
	Cardiac disorders	n (%)	n (%)	n (%)	n (%)	n (%)	n (%)	xx.x (x.x to x.x)	X.XX
	Gastrointestinal disorders	n (%)	n (%)	n (%)	n (%)	n (%)	n (%)	xx.x (x.x to x.x)	x.xx
ARs	Hepatobiliary disorders	n (%)	n (%)	n (%)	n (%)	n (%)	n (%)	xx.x (x.x to x.x)	X.XX

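### Repeated measures ANCOVA/ANOVA over visits has no stated rule for children with a missed visit, and the table footnotes name different methods; a mixed model on all observed visits would settle both

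*Supplement*

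**What the plan says.** Section 7.5 of the SAP covers the primary and secondary outcomes at months 6, 12 and 18. For binocular BCdVA, binocular near VA, reading speed and the EQ-5D-Y VAS and index, "comparisons between the two groups will be performed using repeated measures ANCOVA and 95% CIs", adjusted for baseline. For the symptom items, "Tolerability will be compared between the atropine and placebo groups using repeated measures ANOVA and 95% CI". Section 8.8 repeats the ANCOVA but lists tolerability as plain ANOVA. In section 7.3, "Total hours of outdoor activity and binocular amplitude of accommodation will be compared between the atropine and placebo groups" by repeated measures ANCOVA at all available visits, which in the exploratory table run to month 24.

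The shells in Appendix 1 differ. In the table for months 6, 12 and 18, footnote d attributes the estimates to ANCOVA, and footnote f reads "Mean(SD) and p value from independent samples t-test, no adjustment as tolerability not measured at baseline". The exploratory table also says only ANCOVA. The shells give a separate n for each visit.

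Other outcomes are handled differently. For SER, "results will be used from both eyes and will be compared using GEE (repeated measures model) and 95% CIs", and the other eye-level outcomes also use GEE.

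On missing data, section 7.1 states for the primary outcome that "The principal analysis will be based on complete case data without imputation for those who dropped out of the study". Section 7.6 says that "Sensitivity analyses will be undertaken to assess the impact of missing data for the primary outcome". No such provision covers the outcomes above. Section 3.4 expects little missing data, while section 5 allows for 15% dropout.

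**The concern.** Classical repeated measures ANCOVA or ANOVA needs a full row per child, so one missed visit removes the child from every visit's comparison. The SAP gives no software, estimation method, covariance structure or rule for incomplete children that would rule this out. Per-visit ANCOVA or t-tests, as the footnotes have it, would keep everyone seen at that visit. Two analysts following the same SAP could therefore report different numbers of children, differences and confidence intervals.

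The outcomes concerned bear on a stated secondary objective: tolerability, near vision and reading. Data from a child who later leaves exist at the early visits, and a completers-only analysis would discard them.

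**Working it through.** **The plan's own figures.** Section 5 gives 152 and 76 eyes, an inflation factor of 1.9, 15% dropout and 10% Chinese children. Children needed: 152 × 1.9 / 2 = 144.4 and 76 × 1.9 / 2 = 72.2, total 216.6. Then 216.6 / (1 − 0.15 − 0.10) = 288.8, i.e. 289. The 15% is thus the plan's working dropout rate. This point disputes no stated figure.

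**Assumptions not in the documents.** Dropout is spread evenly over the four post-baseline visits. Each remaining child also misses a visit intermittently with probability m = 0, 3%, 5% or 8%.

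**Retention per visit.** 0.85^(1/4) = 0.9602. Still in the trial at months 6, 12 and 18: 96.0%, 92.2% and 88.5% (about 277, 266 and 256 of 289).

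**If incomplete children are deleted, three visits.**
- Complete fraction = 0.9602³ × (1 − m)³.
- Available at visit k = 0.9602^k × (1 − m).
- SE ratio by simple counts = √(available / complete). This is 1 / [0.9602 × (1 − m)] at month 6 and 1 / (1 − m) at month 18.

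| m | Complete | Children of 289 | SE ratio, month 6 | SE ratio, month 18 |
|---|---|---|---|---|
| 0 | 88.5% | 256 | 1.04 | 1.00 |
| 3% | 81% | 233 | 1.07 | 1.03 |
| 5% | 76% | 219 | 1.10 | 1.05 |
| 8% | 69% | 199 | 1.13 | 1.09 |

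**Four visits (outdoor hours, amplitude of accommodation).** Complete fraction = 0.85 × (1 − m)⁴ = 85%, 75%, 69% and 61%. The month-6 SE ratio is √(0.9602 / 0.85) × (1 − m)^(−1.5) = 1.06, 1.11, 1.15 and 1.20.

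**Bias.** A simulation used 193 and 96 children, no treatment effect, baseline adjustment, between-visit correlation 0.5 or 0.8, 15% dropout, 0%, 5% or 10% intermittent misses, and 400 runs per scenario. Under dropout completely at random none of the methods is biased in expectation. A deliberately strong case let dropout depend on the previous observed value, in opposite directions by arm:
- Complete cases: bias about 0.02 to 0.10 SD.
- Per-visit analysis of everyone seen: close to zero at month 6, about 0.02 to 0.05 SD at month 18.
- Mixed model on all visits: within about 0.01 SD of zero.

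The mixed model's standard errors were at most about 3% smaller than those of the per-visit analysis. The simple-count ratios above are therefore a fair guide to what deletion costs.

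**Text against shells.** For tolerability at months 6, 12 and 18, section 7.5 says repeated measures ANOVA, section 8.8 says ANOVA and footnote f says t-test. For the baseline-adjusted outcomes, sections 7.5 and 8.8 say repeated measures ANCOVA and footnote d says ANCOVA.

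**The case against.** A reader might infer that the plan restricts these analyses to children seen at every visit. The documents do not say so. That reading comes from the method's name, which is also used for models fitted with mixed-model software. The shells show a separate n per visit, and if the footnotes govern, each visit is tested alone and nobody is deleted for missing another. The wording of footnotes d and f matches that of the month-24 table and may simply have been carried over. This stands: listwise deletion is a possible consequence of the text, not a stated rule. It does not remove the need to choose, because text and footnotes lead to different sets of children.

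A reader might also infer that a mixed model avoids dropout bias altogether. It does so only if data are missing at random. If a child leaves because of discomfort never recorded at a visit, the mixed model is biased too. Conversely, a baseline-adjusted complete-case analysis remains valid when missingness depends only on treatment and the adjusted baseline.

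That children who tolerate drops poorly miss more visits is plausible but not shown. Sections 8.4 and 8.10 report drug termination, withdrawals and adverse events by arm, so poor tolerance is also visible elsewhere.

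Finally, no intermittent missed-visit rate appears in the documents, and the affected analyses are labelled additional or exploratory. Both points stand and limit the weight of the finding.

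**Conclusion.** The point holds in a limited form. The SAP names a method that classically discards incomplete children, gives no rule to the contrary, covers these outcomes with no missing-data provision, and contradicts itself in the shells.

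The loss is conditional on deletion. At the planned 15% dropout alone it is small: about 4% in the standard error at month 6 and none at month 18. It reaches 7% to 13% and 3% to 9% only under the assumed 3% to 8% of intermittently missed visits. The outcomes followed to month 24 in one model lose somewhat more.

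The bias figures are illustrative. They need dropout that depends on earlier values and differs by arm, and a mixed model removes that bias only under missing at random. The documents do not support a claim that side effects will be understated.

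SER, axial length, the other eye-level outcomes and the single-visit secondary comparisons at month 24 are not touched.

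**What to change.** In sections 7.3, 7.5 and 8.8, replace repeated measures ANCOVA/ANOVA with a likelihood-based linear mixed model:
- fixed effects for treatment, visit and treatment-by-visit, plus the baseline value where one is collected;
- unstructured within-child covariance, with a stated fallback if it does not converge;
- all available visits, with no deletion of children who miss one.

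Report the treatment difference at each visit with its 95% CI, and state that validity rests on missing at random.

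Correct footnotes d and f of the table for months 6, 12 and 18, and the ANCOVA footnote of the exploratory table, to name this model.

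The cost is SAP wording and a different procedure call. No new data are needed.
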